5.1 Analysis Datasets

The following samples are defined for this trial:

- Randomized: consists of all subjects who are randomized into this trial.
- Safety Analysis Set (SAS): consists of all subjects who are administered at least one dose of IMP.
- Full Analysis Set (FSA): consists of all subjects who are in the Randomized Sample, take at least one dose of IMP, and have a baseline and at least one postbaseline evaluation of the CDAI score.

In general, baseline of an efficacy endpoint is defined as the last observation of the endpoint before the subject takes the first dose of IMP.

The core dataset for all efficacy analyses is based on the intent-to-treat (ITT) population, which will consist of all randomized subjects who take at least one dose of IMP. The Full Analysis Set, which is identical to the Efficacy Sample, will also be used in the efficacy analyses. As described below, in order to handle missing data and restrictions imposed by

different types of analyses (eg, change from baseline analysis), other datasets derived from the ITT population will be used for the efficacy analyses.

5.2 Handling of Missing Data

The estimand defining the treatment effect of interest in the protocol uses a mixture of composite strategy and treatment policy strategy specified in the ICH E9 addendum. Subjects who increase dosages of baseline Crohn's disease medications or take a new therapy for Crohn's disease during the trial are considered as treatment failures (non-responders) in the ITT analysis of the primary and secondary endpoints, while these subjects are encouraged to stay in the trial for continuous data collection. These data collected after subjects change their baseline Crohn's disease medication will only be provided in data listings, but not used in the primary and secondary efficacy analyses. In addition, subjects who withdraw from the trial early are considered as treatment failures (non-responders) in the ITT analysis of all of the primary and secondary endpoints. Subjects who discontinue IMP during the trial with no baseline Crohn's disease medication dosage increases and/or new therapy for Crohn's disease through Week 12 are encouraged to stay in the trial and take primary and secondary endpoint evaluations at Week 12 for efficacy analyses. Hence, missing data at Week 12 due to subjects' change of baseline Crohn's disease medication and early withdrawal is handled by an ITT analysis with all these subjects treated as treatment failures (nonresponders).

For CDAI-related endpoints, if a subject has a Week 12 evaluation but a component of the score is missing, the value of the component in the most recent previous visit will be used for the calculation of the score and the endpoint if no more than 2 components of the CDAI score are missing. For a CDAI assessment, if more than 2 components of the score are missing, the CDAI score will be set to missing. This approach is conservative since subjects randomized to OPS-2071 treatment groups are expected to have their Crohn's disease symptoms improved over time. No component is allowed to be missing in a PRO-related endpoint. The abdominal pain and stool frequency scores of PRO-2 are averaged over a 7-day period from the subject's diary.

6 Study Conduct

6.1 Subject Disposition

The number of subjects who have been randomized, the number of subjects who are treated, and the number of subjects who discontinue from the trial, together with the reasons for discontinuation taken from the eCRF status page will be provided.

6.2 Prior and Concomitant Medications

The proportion of subjects taking concomitant medications will be tabulated for all randomized sample for prior to, during and after the trial medication.

6.3 Protocol Deviations

Protocol deviations data will be summarized by type of deviations (eg, deviations in entry criteria, dosing, concomitant medication, procedural, etc) by trial center. In addition, a subject listing will be provided describing the deviations for each subject.

7 Demographic and Baseline Characteristics

Demographics, disease severity, baseline characteristics, and medical history at (predose) baseline will be summarized by descriptive statistics; eg, proportion, mean, median, standard deviation, and minimum and maximum values. These summary statistics will be reviewed to identify any potential lack of balance between the treatment groups.

8 Efficacy Analysis

8.1 Primary Efficacy Endpoint

The primary efficacy endpoint is percentage of subjects who, at Week 12, achieve clinical remission (defined as a CDAI score < 150).

8.1.1 Primary Estimand

The primary objective is to investigate the therapeutic effect of OPS-2071 add-on therapy administered orally for 12 weeks in subjects with Crohn's disease showing symptoms of active inflammation despite ongoing treatment. The primary estimand defining the treatment effect of interest in the protocol uses a mixture of composite strategy and treatment policy strategy specified in the ICH E9 addendum.² Two types of intercurrent events are accounted for by these two strategies:

- Increasing dosages of baseline Crohn's disease medications or taking a new therapy for Crohn's disease: The occurrence of this intercurrent event may provide meaningful information on the treatment effect of interest such as lack of efficacy, and will be taken to be a component of the variable for the primary estimand. Following the composite strategy, the primary estimand assess the treatment effect based on a composite variable which combines percentage of subjects achieve clinical remission at week 12 and the intercurrent event of the changes of the medications for Crohn's disease. The subjects with this type of intercurrent event will be considered as treatment failures.

- Early withdrawal from the trial: Interest lies in the treatment effect regardless of this intercurrent event. Following treatment-policy strategy, occurrence of the early withdraw intercurrent event is ignored, and the primary estimand is then the difference between treatment groups in percentage of subjects who achieve clinical remission at week 12, regardless of whether or not early withdraw had occurred.

The primary estimand for this trial is defined by the following components:

- Population: subjects with Crohn's disease and showing symptoms of active inflammation despite ongoing treatment who have met the protocol-defined inclusion/exclusion Criteria
- Endpoint: the percentage of subjects who, at Week 12, achieve clinical remission (defined as a CDAI score < 150)
- Intercurrent Events: increase dosages of baseline Crohn's disease medications or take a new therapy for Crohn's disease during the trial, and early withdraw from the trial
- Population-level summary: difference in clinical remission proportions between OPS2071 and placebo

Subjects who increase dosages of baseline Crohn's disease medications or take a new therapy for Crohn's disease during the trial and subjects who withdraw from the trial early are considered as treatment failures in the ITT analysis of all of the primary and secondary response/remission endpoints. Subjects who discontinue IMP during the trial with no baseline Crohn's disease medication dosage increases and/or new therapy for Crohn's disease through Week 12 are encouraged to stay in the trial and take primary and secondary endpoint evaluations at Week 12 for efficacy analyses. Hence, missing data at Week 12 due to subjects' early withdrawal is handled by an ITT analysis with all subjects who early withdraw from the trial treated as treatment failures.

8.1.2 Primary Efficacy Analysis

Logistic regression with terms of treatment group, the randomization stratification factors, location of disease, country, age, sex, disease duration, smoking habit, and baseline CDAI, and baseline CDAI with CDAI stratification factor interaction will be applied to the primary endpoint. The FAS will be used in the efficacy analysis.

The primary analysis of this trial is comparison of the pooled OPS-2071 600 mg BID and 300 mg BID treatment groups with placebo in the primary endpoint of clinical remission.

If this analysis is significant at a 2-sided alpha level of 0.05, comparisons to OPS-2071 600 mg BID versus placebo and OPS-2071 300 mg BID versus placebo in the primary endpoint will be conducted with a 2-sided alpha level of 0.05 in each comparison. If the comparison of the pooled OPS-2071 dose groups versus placebo in the primary endpoint is significant at a 2-sided alpha level of 0.05, and a comparison, say, OPS-2071 600 mg BID versus placebo, is also significant at a 2-sided alpha level of 0.05, the null hypothesis of equal response of OPS-2071 600 mg BID and placebo in the primary endpoint will be considered rejected with an experiment-wise Type I error of 0.05.

The comparison between OPS-2071 150 mg BID versus placebo in the primary endpoint is considered as a secondary analysis and the details are provided in section 8.4.

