	
• Subjects with inadequate organ function, as follows:
• Serum creatinine $> 1.5 \times$ the upper limit of normal (ULN)• Aspartate aminotransferase or alanine aminotransferase levels $> 1.5 \times$ ULN• Total bilirubin $> 1.5 \times$ ULN. Elevated unconjugated bilirubin related to Gilbert's syndrome is allowed.• Known hypersensitivity to quinolones or other significant adverse reaction to quinolones.• Subjects with a history of treatment failure with 2 or more biologics.
Note: The rationale for excluding subjects who have failed 2 or more biologics is due to the fact that they may represent an especially difficult-to-treat population (ie, medically refractory) that may not benefit substantially from fluoroquinolones and/or will likely need additional, more invasive treatment (ie, surgical resection).
• Subjects with risk factors for tendon rupture (ie, psoriasis, ankylosing spondylitis, competitive athletes, renal failure, diabetes mellitus) or who have a history of tendon rupture and/or ongoing tendinopathy.• Subjects with systolic blood pressure > 150 mmHg or diastolic blood pressure > 90 mmHg.• Subjects taking quinidine, procainamide, disopyramide, encainide, flecainide, sotalol, amiodarone, ibutilide, dronedarone, or propafenone.
Trial Site(s):	Approximately 100 trial sites in the United States, Canada, and Europe.

Protocol 341-201-00004

Investigational Medicinal Product(s), Dose, Dosage regimen, Treatment period, Formulation, Mode of Administration:	Eligible subjects will be randomized on Day 1 to 1 of 4 treatments: placebo BID, OPS-2071 150 mg BID, OPS-2071 300 mg BID, or OPS-2071 600 mg BID. The investigational medicinal product (IMP) will be supplied as 150-mg and 300-mg OPS-2071 tablets, and matching placebo tablets. The IMP will be administered as oral tablets, BID (8 to 12 hours apart), starting on Day 1 for a total of 12 weeks. The timing of the first dose of IMP will be at the subject's or trial site's discretion. Each subject will take 6 tablets daily (to maintain blinding); 3 tablets for the morning dose and 3 tablets 8 to 12 hours later. The IMP will be administered with up to 240 mL (8 fluid ounces) of still water, at least 1 hour before or after a meal. Water intake will be restricted for 1 hour before and after the morning dose of IMP at Day 1 and Week 6 for the robust blood sampling.

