3.3 Trial Population

Approximately 240 male and female subjects between the ages of 18 and 70 (inclusive), with Crohn's disease and showing symptoms of active inflammation despite ongoing

treatment, will be randomized. Active mucosal inflammation will be confirmed by centrally read ileocolonoscopy. Discontinued or withdrawn subjects will not be replaced.

4 Sample Size

For the primary endpoint of clinical remission (CDAI score < 150), assuming a 40% response rate in the OPS-2071 600 mg BID and 300 mg BID dose groups and a 20% response rate in the placebo group, 60 randomized subjects per treatment group would provide 80% power to detect a treatment difference between the OPS-2071 pooled dose groups (600 mg BID and 300 mg BID) and the placebo group in the primary endpoint, using a 2-sided alpha of 0.05. The total sample size of the trial is 240 randomized subjects with 1:1:1:1 randomization to OPS-2071 600 mg BID, 300 mg BID, or 150 mg BID, or placebo BID. The power of individual dose comparison with placebo under the same assumption is 67%.

For the secondary endpoint of endoscopic response, assuming a 26.5% response rate in the OPS-2071 600 mg BID and 300 mg BID dose groups and a 10% response rate in the placebo group, 60 subjects per treatment group would provide 80% power for the comparison between the OPS-2071 pooled dose groups (600 mg BID and 300 mg BID) and the placebo group, and 65% power for the individual dose comparison with placebo, using a 2-sided alpha of 0.05.

5 Statistical Analysis Datasets

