8.1.6 Subgroup Analysis

Subgroup analysis of the percentage of subjects who achieve clinical remission at week 12 will be conducted by gender, race (Caucasian and Non-Caucasian), age (18 to < 40, 40 to < 50, and at least 50), and region (US and non-US) using logistic regression with terms of treatment group, the randomization stratification factors, location of disease, disease duration, smoking habit, and baseline CDAI, and baseline CDAI with CDAI stratification factor interaction.

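### The primary logistic model has too many covariates for its expected events: simulated Type I error is about 6–7% instead of 5%, and the conditional odds ratio is biased upward

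*SAP*

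**What the plan says.** SAP 8.1.2 and Protocol 7.4.1 specify one logistic regression for Week 12 remission. Besides treatment and the randomization factors (CDAI in two levels, medication status in three), it includes "location of disease, country, age, sex, disease duration, smoking habit, and baseline CDAI, and baseline CDAI with CDAI stratification factor interaction". The Protocol synopsis describes "Approximately 100 trial sites in the United States, Canada, and Europe" but gives no number of countries.

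The documents do not state:
- the levels of disease location or smoking;
- the test statistic;
- whether the pooled contrast is one term or a combination of dose terms;
- what to do about a country with few subjects, separation or non-convergence.

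The pooled 600 mg and 300 mg comparison with placebo is tested first, at 0.05 two-sided. SAP 8.1.2 and 8.4 claim experiment-wise control at 0.05 for the chain that follows. SAP section 4 sizes the trial "assuming a 40% response rate in the OPS-2071 600 mg BID and 300 mg BID dose groups", against 20% on placebo, stating that "60 randomized subjects per treatment group would provide 80% power to detect a treatment difference". It gives 67% for a single dose.

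The same model form is used again in SAP 8.2.1 for endoscopic response, with baseline SES-CD in place of baseline CDAI. It is also refitted to the imputed data in 8.1.4. SAP 8.1.5 adds a CMH test on the stratification factors, naming only individual doses against placebo. SAP 8.1.1 declares the summary measure to be a difference in proportions. SAP 8.1.6 splits geography into US and non-US for subgroups, and its model leaves out country, age and sex.

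**The concern.** Maximum-likelihood logistic regression is biased when there are few events per parameter. Coefficients drift away from zero and the test statistic becomes too large. The pooled comparison opens the gatekeeping chain, so its actual level limits what can be claimed for the chain when no dose works. Later tests on binary endpoints use the same kind of model. If the first test runs above 5%, the claimed experiment-wise level is not met, and a reported adjusted odds ratio would flatter the drug.

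**Working it through.** **1. The plan's own power.** With n = 120 and 60, rates of 40% and 20% and a pooled rate of 60/180 = 0.333:

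Φ{[0.20 − 1.96·√(0.333·0.667·(1/60 + 1/120))] / √(0.2·0.8/60 + 0.4·0.6/120)} = Φ{(0.20 − 0.146)/0.0683} = Φ(0.789) = 0.785.

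The arcsine formula gives 0.799 and the likelihood-ratio test 0.801, so 80% reproduces. For 60 versus 60 the first formula gives 0.670, the stated 67%. These are unadjusted two-proportion tests, so the sample-size section says nothing about how the covariate model behaves.

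**2. Parameters.** Intercept 1, treatment 1–3, CDAI stratum 1, medication status 2, location 2–3 (assumed levels), age 1, sex 1, duration 1, smoking 1–2 (assumed), baseline CDAI 1, interaction 1. This totals 13–17, plus the number of countries minus 1:
- 3 countries: 15–19
- 10 countries: 22–26
- 16 countries: 28–32
- 25 countries: 37–41

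**3. Events.** Null: 240 × 0.20 = 48. Design rates: 60 × 0.20 + 120 × 0.40 = 60, plus 12–24 from the 150 mg arm at an assumed 20–40%, giving 72–84. Null events per parameter are 48/15 = 3.2 at best, 48/22 = 2.2 with 10 countries and 48/28 = 1.7 with 16.

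**4. Type I error.** Simulated with 10,000 trials per scenario (Monte Carlo SE about 0.24 points). Assumptions: 240 subjects, baseline CDAI moderately prognostic, other covariates not prognostic, unequal country sizes, no dropout.

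| Assumed countries | Wald | Likelihood ratio |
|---|---|---|
| 3 | 6.0% | 6.7% |
| 9–10 | 5.9% | 6.5–6.6% |
| 16 | 6.2% (6.5% if equal-sized) | 6.9–7.0% (7.2% if equal-sized) |
| 25 | 6.7% | 7.6% |

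The reduced model (treatment, stratification factors, baseline CDAI) gives 4.8–5.1%. If only the three primary arms are fitted (180 subjects, 36 null events, 10–16 countries), the planned model gives 6.2–6.8% (Wald) and 7.0–7.6% (likelihood ratio).

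**5. Effect estimate.** The true log odds ratio is ln[(0.4/0.6)/(0.2/0.8)] = ln 2.667 = 0.981. The mean estimate is 1.122 with 10 countries (e^1.122 = 3.07; 3.07/2.667 = 1.15) and 1.152 with 16 (3.16; ratio 1.19). The reduced model gives 1.02–1.03, an odds ratio about 4–5% high.

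**6. How much is due to country.** In a separate run with 12 countries (6,000 null trials), Type I error was 6.3% for the planned model, 5.5% with country removed and 4.9% for the reduced model. Mean log odds ratios (3,000 trials) were 1.117, 1.059 and 1.020. The bias remaining without country is (1.059 − 0.981)/(1.117 − 0.981) = 0.078/0.136, or 57%.

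**7. Power.** The planned model has 74.2–74.7% (Wald; 9 and 16 countries) and the reduced model 74–76%. Another run gave 76.8% against 77.1%. The absolute level depends on the assumed covariate effects and does not contradict the plan's 80%. Only the near-zero difference is informative.

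**8. Endoscopic response.** Null events are 240 × 0.10 = 24. With 12 assumed countries, simulated Type I error was 6.3%, and 92% of trials had at least one country with no responders or only responders.

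**The case against.** The fair defence is that the excess is small, about 1–2 points in a phase 2 proof-of-concept trial, and that it rests on a simulation whose country count is not in the documents. One 4,000-trial run with three countries gave only 5.5%, against 4.6% for the reduced model. The covariates are prespecified, and a CMH test on the stratification factors alone is already planned. The trial stopped after three subjects.

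The modest size is conceded. The direction does not depend on the country count. The CMH test does not name the pooled primary contrast, so it does not protect it. Early termination means no result is affected, but it does not make the written analysis sound.

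Several stronger readings are tempting and are not supported:
- **A large, known parameter count.** A reader might infer one from the hundred sites. Site is not a model term, and the site count does not give the country count.
- **A specified Wald test.** The plan names no statistic. The likelihood-ratio test does no better, so this changes the description and not the finding.
- **Breakdown of the treatment estimate.** A country without remitters gives a divergent country coefficient, and its subjects then add almost nothing. The treatment contrast stays finite. The problem found here is ordinary small-sample bias.
- **Inflation of the declared effect measure.** The declared summary is a difference in proportions. The bias shown is on the conditional odds ratio, and the SAP does not say how the model yields the difference.

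**Conclusion.** The concern holds at moderate size. The planned maximum-likelihood test runs at about 6–7% for 3–25 assumed countries, reaching 7.6% for the likelihood-ratio test with 25. With 10–16 countries and all four arms fitted, the conditional odds ratio is about 15–19% too high. The whole covariate list is responsible, with country adding to it. The figures assume the covariate levels, country sizes and prognostic strengths listed above, and no dropout. The parameter count itself cannot be fixed from the documents. The finding concerns the plan as written.

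**What to change.** In SAP 8.1.2, Protocol 7.4.1 and the synopsis, define the primary model as treatment, the two randomization stratification factors and continuous baseline CDAI. If geography is wanted, add the US/non-US split already defined in SAP 8.1.6. Move the full covariate list to a sensitivity analysis, with a stated rule for sparse countries. Extend the CMH analysis in SAP 8.1.5 to the pooled 600 mg and 300 mg contrast. Make the same reduction for endoscopic response in SAP 8.2.1 and Protocol 7.4.2, keeping baseline SES-CD, because events are fewer there. The refit in SAP 8.1.4 should follow the new primary model.

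The cost is a change of wording. The primary model would no longer adjust for country and the minor covariates, which gives up some precision if one of them is strongly prognostic; the simulations assumed none was. A Firth-penalised fit of the full list is an alternative. It held Type I error at 4.1–4.5% with an essentially unbiased log odds ratio (0.985–0.988), but its power was 67–69%, against 74–76% for the reduced model.

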7.2 Datasets for Analysis

The following samples are defined for this trial:

- Randomized: consists of all subjects who are randomized into this trial.
- Safety: consists of all subjects who are administered at least one dose of IMP.

Protocol 341-201-00004

- Efficacy: consists of all subjects who are in the Randomized Sample, take at least one dose of IMP, and have a baseline and at least one postbaseline evaluation of the CDAI score.

In general, baseline of an efficacy endpoint is defined as the last observation of the endpoint before the subject takes the first dose of IMP.

The core dataset for all efficacy analyses is based on the intent-to-treat (ITT) population, which will consist of all randomized subjects who take at least one dose of IMP. The Full Analysis Set, which is identical to the Efficacy Sample, will also be used in the efficacy analyses. As described below, in order to handle missing data and restrictions imposed by different types of analyses (eg, change from baseline analysis), other datasets derived from the ITT population will be used for the efficacy analyses.

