7.3 Handling of Missing Data

7.3.1 Estimand and Strategies for Addressing Intercurrent Events

The estimand defining the treatment effect of interest in the protocol uses a mixture of composite strategy and treatment policy strategy specified in the ICH E9 addendum.¹⁶ Subjects who increase dosages of baseline Crohn's disease medications or take a new therapy for Crohn's disease during the trial are considered as treatment failures (nonresponders) in the ITT analysis of the primary and secondary endpoints, though they are encouraged to stay in the trial to be followed continuously. Their efficacy evaluations after the change of baseline Crohn's disease medications will not be included in the efficacy analysis but will be provided in the listings. In addition, subjects who withdraw early from the trial are also considered as treatment failures (nonresponders) in the ITT analysis of all of the primary and secondary endpoints. Subjects who discontinue IMP during the trial with no baseline Crohn's disease medication dosage increases and/or new therapy for Crohn's disease through Week 12 are also encouraged to stay in the trial and take primary and secondary endpoint evaluations at Week 12 for efficacy analyses. Hence, missing data at Week 12 due to subjects' early withdrawal and change of baseline Crohn's disease medications is handled by an ITT analysis with all subjects treated as treatment failures (nonresponders).

For CDAI-related endpoints, if a subject has a Week 12 evaluation but a component of the score is missing, the value of the component in the most recent previous visit will be used for the calculation of the score and the endpoint if no more than 2 components of the CDAI score are missing. For a CDAI assessment, if more than 2 components of the score

Protocol 341-201-00004

are missing, the CDAI score will be set to missing. This approach is conservative since subjects randomized to OPS-2071 treatment groups are expected to have their Crohn's disease symptoms improved over time. No component is allowed to be missing in a PRO-related endpoint. The abdominal pain and stool frequency scores of PRO-2 are averaged over a 7-day period from the subject's diary.

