7.4.1 Primary Endpoint Analysis

The primary endpoint of the trial is the percentage of subjects who, at Week 12, achieve clinical remission (CDAI score < 150).

Protocol 341-201-00004

Logistic regression with terms of treatment group, the randomization stratification factors, location of disease, country, age, sex, disease duration, smoking habit, and baseline CDAI, and baseline CDAI with CDAI stratification factor interactions will be applied to the primary endpoint. The efficacy sample will be used in the efficacy analysis. Remission and nonremission subjects (ie, treatment failures) are defined as follows:

- Subjects who complete the trial and meet the primary endpoint definition at Week 12 without increasing dosages of baseline Crohn's disease medications or taking a new medication for Crohn's disease during the double-blind treatment period will be considered as remission subjects for the endpoint.
- Subjects who increase dosages of baseline Crohn's disease medications or take a new medication for Crohn's disease during the double-blind treatment period, or subjects who withdraw from the trial during the double-blind period, in addition to the subjects who fail to meet the primary endpoint at Week 12, will be considered as nonremission subjects for the endpoint.

The primary analysis of this trial is comparison of the pooled OPS-2071 600 mg BID and 300 mg BID treatment groups with placebo in the primary endpoint of clinical remission. If this analysis is significant at a 2-sided alpha level of 0.05, comparisons to OPS-2071 600 mg BID versus placebo and OPS-2071 300 mg BID versus placebo in the primary endpoint will be conducted with a 2-sided alpha level of 0.05 in each comparison. If the comparison of the pooled OPS-2071 dose groups versus placebo in the primary endpoint is significant at a 2-sided alpha level of 0.05, and a comparison, say, OPS-2071 600 mg BID versus placebo, is also significant at a 2-sided alpha level of 0.05, the null hypothesis of equal response of OPS-2071 600 mg BID and placebo in the primary endpoint will be considered rejected with an experiment-wise Type I error of 0.05.

The comparison between OPS-2071 150 mg BID versus placebo in the primary endpoint is considered as a secondary analysis and is provided in [Section 7.4.2](#).

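### The primary analysis set is stated two ways: the model is assigned to the FAS, while the failure rule for early withdrawals promises an ITT analysis

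*SAP*

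**What the plan says.** Both documents attach one analysis set to the primary model. SAP 8.1.2: "The FAS will be used in the efficacy analysis". Protocol 7.4.1: "The efficacy sample will be used in the efficacy analysis". These are the same set; SAP 5.1 says so and adds "The Full Analysis Set, which is identical to the Efficacy Sample, will also be used in the efficacy analyses". To belong, a randomized subject must "take at least one dose of IMP, and have a baseline and at least one postbaseline evaluation of the CDAI score".

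The dataset and missing-data sections point elsewhere. Protocol 7.2 (repeated in SAP 5.1): "The core dataset for all efficacy analyses is based on the intent-to-treat (ITT) population", defined as all randomized subjects with at least one dose and with no CDAI requirement. Protocol 7.3.1 says that Week 12 data missing through early withdrawal or a change of Crohn's medication "is handled by an ITT analysis with all subjects treated as treatment failures (nonresponders"). SAP 5.2 repeats this, and SAP 8.1.1 applies it to all who withdraw early.

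Protocol 7.4.1 also lists "subjects who withdraw from the trial during the double-blind period" among the nonremission subjects, in the same passage that names the efficacy sample. The failure rule therefore appears with both sets.

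**The concern.** Two readings are open. One is a FAS analysis with failures imputed inside it. The other is an ITT analysis in which every dosed leaver counts.

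They part on a dosed subject with no post-baseline CDAI evaluation, who is a failure under the rule but outside the FAS. A second group is uncertain. The diary restarts on Day 1 (Protocol 3.7.2.4). A leaver who attends with fewer than five diary days has three CDAI components set to missing, and so the score too (SAP 8.1.3, items 3 and 4). Whether that subject enters the FAS depends on whether an evaluation means a visit or a computable score; the definition does not say.

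FAS membership depends on data collected after randomization. Dropping nonremitters from the denominator raises the arm's rate, so unequal early loss favours the arm that loses more. The pooled comparison gates every later test in SAP 8.4, and SAP 8.2.1 carries the same procedure to endoscopic response. Two analysts following different sections could run the gate on different denominators.

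**Working it through.** **Inputs.** Sample size section (Protocol 7.1, SAP 4): 60 randomized per group, so 60 placebo v 120 pooled active; remission 20% v 40%; endoscopic response 10% v 26.5%; two-sided alpha 0.05. The share of dosed subjects outside the FAS (dP placebo, dA active) is not in the documents, so 0–5% is assumed, with every such subject a nonremitter. All figures are unadjusted; the planned model is covariate-adjusted.

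**The plan's own figures.** With d the difference in rates, s0 the pooled-variance standard error and s1 the unpooled one:

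rejection in favour of drug = 1 − Φ[(1.96·s0 − d)/s1]

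For 20% v 40%, 60 v 120: pooled rate 0.3333, s0 = 0.0745, s1 = 0.0683, power 78.5% (plan: 80%). For 60 v 60: 67.0% (plan: 67%). For endoscopic response: 75.6% pooled (plan: 80%) and 65.1% per dose (plan: 65%). An arcsine formula gives 79.9% and 79.1% for the two pooled comparisons, so no error in the power statement is claimed. The calculation uses all randomized subjects with no allowance for loss, which fits an ITT denominator better than a FAS.

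**Effect on the estimate.** FAS rate = ITT rate / (1 − loss). Active: 0.40/0.98 = 0.4082; 0.40/0.95 = 0.4211. Placebo: 0.20/0.98 = 0.2041; 0.20/0.95 = 0.2105.

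**Effect on error.** Set both ITT rates to 20% and use group sizes 60(1 − dP) and 120(1 − dA). Example at 0%/2%: rates 0.2000 and 0.2041, d = 0.0041, s0 = 0.06378, s1 = 0.06362, so 1 − Φ(1.90) = 0.0287.

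| Loss, placebo/active | FAS difference (ITT 20.0 points) | Error for drug | Error against drug | Two-sided |
|---|---|---|---|---|
| 0%/0% | 20.0 | 2.5% | 2.5% | 5.0% |
| 2%/2% | 20.4 | 2.5% | 2.5% | 5.0% |
| 0%/2% | 20.8 | 2.9% | 2.1% | 5.0% |
| 2%/0% | 19.6 | 2.2% | 2.9% | 5.1% |
| 0%/5% | 22.1 | 3.5% | 1.6% | 5.2% |
| 5%/0% | 18.9 | 1.8% | 3.7% | 5.5% |

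In whole subjects: losing 2 of 120 active and none of 60 placebo gives 0.40 × 120/118 = 0.4068, a difference of 20.7 points and 2.8% error for drug.

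Simulation of the same test (400,000 trials) gives slightly lower error for drug: 2.3% with no loss, 2.6% at 0%/2%, 3.3% at 0%/5% and 1.5% at 5%/0%.

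**Endoscopic response** (ITT difference 16.5 points). At 0%/2%: 0.265/0.98 − 0.10 = 17.0 points, error for drug 2.7%. At 0%/5%: 17.9 points, 3.1%. No rates are planned for PRO-2 remission, so none is computed.

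**A constructed borderline case.** Placebo 12/60 v active 40/120 gives z = 1.86, p = 0.063. Removing three never-evaluated active nonremitters (40/117) gives z = 1.96, p = 0.0498. Removing two gives p = 0.054.

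**The case against.** The two sections that specify the primary test agree with each other: both name the FAS. The FAS is a subset of the ITT population, and the dataset sections allow further datasets derived from ITT. The ITT wording in the missing-data sections can be read as a label for the failure rule, applied within the FAS; Protocol 7.4.1 puts rule and set together. On that view this is loose terminology.

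The affected group is also close to empty. Leavers, including those who fully withdraw consent, are assigned an End of Treatment visit (Protocol 3.8.3.2) that includes a CDAI (Table 3.7-1, footnote b). The rule for incomplete scores in SAP 8.1.3 treats an evaluation as distinct from its score, which suggests that an attended visit qualifies. The loss rates are assumed, two-sided error hardly moves, and the borderline example was chosen to be borderline. Naming one set would be enough; the PRO-2 rule is another matter.

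Most of this stands as a limit on size. It does not remove the conflict. No section gives either set precedence, and saying that the FAS will also be used does not do so. Applying the rule inside the FAS breaks the promise in SAP 8.1.1 for leavers outside it. The placebo-based imputation (SAP 8.1.4.1) and the CMH analysis (SAP 8.1.5) name no set. The PRO-2 change follows from the fix: a logistic regression drops any subject whose status is missing.

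**Conclusion.** The concern holds. The plan gives two incompatible denominators for the primary test, and following SAP 8.1.2 literally drops subjects whom SAP 8.1.1 counts as failures.

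The likely effect is small. With one-sided loss of 2%, the estimate moves by less than one point and error for drug by about 0.4 points. The 5% one-arm case is the upper end shown, and no document supports it. Equal loss leaves type I error unchanged, and unequal loss can bias for or against the drug. These figures assume that those lost are all nonremitters and that the test is unadjusted.

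The reason to correct it is that the primary analysis should be reproducible from the text. SAP 11 states that the planned analyses will not be performed because only three subjects were randomized, so no reported result is affected.

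**What to change.** In SAP 8.1.2 and Protocol 7.4.1, name the ITT population already defined (randomized and dosed) as the primary set for the primary and the binary secondary endpoints. State that every withdrawal and every missing Week 12 status counts as nonremission or nonresponse. This also settles completers with a missing Week 12 score, and it requires amending SAP 8.2.2 item 3, which now sets PRO-2 remission to missing.

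Keep the FAS as a supportive analysis. State whether an evaluation in its definition requires a computable CDAI score, name the set used in SAP 8.1.4.1, and report by arm how many ITT subjects fall outside the FAS.

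The cost is wording, plus slightly lower displayed rates, including for PRO-2. If the planned 20%/40% were meant as FAS rates, ITT rates are those times (1 − loss). Primary power, by the normal approximation, then falls from 78.5% to 77.2% at 2% loss per arm (19.6% v 39.2%) or 75.2% at 5% (19% v 38%). Endoscopic response falls from 75.6% to 74.4% or 72.6%. The ITT set still omits randomized but undosed subjects.

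A separate point, not counted here: SAP 8.1.1 labels early withdrawal as treatment policy while counting it as failure; the label should be composite.
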